5.8 Duration of Follow-up

Patients who receive the study therapy will be observed post-surgery for 30-60 days or resolution of AEs, whichever comes later, then yearly for recurrence and survival status for 5 years. Patients who received adjuvant PD 0332991 will be followed as described in Section 10.3 during adjuvant PD 0332991 therapy, then yearly following completion of PD 0332991 to complete a total of 5 years of follow-up post-surgery.

6.0 DOSE DELAYS/DOSE MODIFICATIONS

Table 3. Dose Modification Table.

Dose Level	PD 0332991 Days 1-21 of each 28-day cycle	Anastrozole (daily)
1 (starting dose)	125 mg/day	1 mg/day
-1	100 mg/day	1 mg/day
-2	75 mg/day	1 mg/day

Note that PD 0332991 dose reduction below 75 mg/day is not allowed

6.1 Dose Modifications for Anastrozole

No dose adjustment is permitted for anastrozole but interruptions are allowed per physician discretion. During adjuvant phase, switching to another hormonal therapy is allowed.

6.2 Dose Modifications for PD 0332991

Patients will be monitored for toxicity and the dose of PD 0332991 may be adjusted as indicated in Table 3. Dose reduction by 1, and if needed, 2 dose levels will be allowed depending on the type and severity of toxicity encountered (Table 4). Patients requiring more than 2 dose reductions will be discontinued from the study.

Recommended dose reductions for PD 0332991 are detailed in Table 4. Doses may be held as needed for toxicity resolution during a cycle. Doses omitted for toxicity are not replaced or restored within the same cycle (meaning that the cycle remains 28 days regardless of the number of doses of taken).

Treatment with PD 0332991 should be permanently discontinued if toxicity has not recovered to grade ≤ 2 within two weeks (including the scheduled 1-week off treatment period within a cycle).

Table 4. PD 0332991 Dose Modifications Based on Worst Treatment-Related Toxicity in the Previous Cycle

Worst Toxicity During Previous Cycle	Action	New Dose Level
Grade 4 neutropenia	Hold until ANC $\geq 1000/\text{mm}^3$	Decrease by one dose level
Grade 4 thrombocytopenia	Hold until platelets $\geq 50,000$	Decrease by one dose level
Grade 3 neutropenia associated with a documented infection or fever $\geq 38.5^\circ\text{C}$	Hold until ANC $\geq 1000/\text{mm}^3$ without fever	Decrease by one dose level
Grade 3 neutropenia without fever	Hold until ANC $\geq 1000/\text{mm}^3$	1 st occurrence: resume at the same dose 2 nd occurrence: decrease by one dose level 3 rd occurrence: decrease by one dose level
Grade ≥ 3 non-hematologic toxicity (includes nausea, vomiting, diarrhea, and hypertension only if persisting despite maximal medical treatment)	Hold until recover to \leq grade 1 (or \leq grade 2 if investigator does not consider the AE a safety risk)	Decrease by one dose level
Inability to deliver at least 80% of the planned dose of PD 0332991 or anastrozole due to adverse events possibly related to study treatment		Decrease by one dose level
Grade ≥ 2 non-hematologic toxicity (except alopecia) that persists longer than 4 weeks despite maximal supportive care and is unacceptable to patient and/or investigator		Decrease by one dose level

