5.0 TREATMENT PLAN

5.1 Neoadjuvant Treatment

Treatment will be administered on an outpatient basis. Patients will be instructed to make use of medication diaries (Appendices D and E) to act as a records for administration of PD 0332991 and anastrozole. Appropriate dose modifications are described in Section 6.0. No investigational or commercial agents or therapies other than those described below may be administered with the intent to treat the patient's malignancy.

Cycle 0 (Only applicable for PIK3CA Mutant and WT cohorts)

Before Cycle 1 Day 1 starts, patients who enrolled in the PIK3CA mutant or WT cohort should have completed Cycle 0. Cycle 0 therapy is 28 days of anastrozole (1mg PO daily) and, if premenopausal, goserelin 3.6mg SC every 28 days.

Cycles 1-5

Treatment with PD 0332991 combined with anastrozole (and goserelin if premenopausal) is to be 4 28-day cycles followed by a fifth cycle of 10-12 days duration consisting of daily PD 0332991 and anastrozole, with the last dose of both drugs to be given the day before surgery.

REGIMENT DESCRIPTION				
Agent	Dose	Route	Schedule	Cycle Length
PD 0332991	125 mg	PO	Daily (Days 1-21)	Cycles 1-4: 28 days
Anastrozole	1 mg	PO	Daily (Days 1-28)	Cycle 5: 10-12 days
Goserelin*	3.6 mg	SC	Q28 days	Adjuvant treatment: 28 days

* only if premenopausal; although it is preferred to be given on Day 1 of each cycle, it may be administered any day of the cycle to accommodate the Q28-day cycle for goserelin.

PD 0332991 should be taken with food. Anastrozole should be taken daily with or without food.

For both PD 0332991 and anastrozole:

- If a patient misses a day's dose entirely, she must be instructed not to make it up the next day but just take her regular dose the following day.
- If a patient vomits anytime after taking a dose, she must be instructed not to make it up but to resume subsequent doses the next day as prescribed.
- If a patient inadvertently takes an extra dose during a day, she must be instructed to not take the next day's dose.

Special Considerations for Cycle 5

Cycle 5 Day 1 of PD 0332991 may be delayed by up to 3 weeks to allow ANC to recover to $\geq 1500/\text{mcL}$ and platelets to recover to $\geq 100,000/\text{mcL}$ and other treatment related AEs

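### Table 4 gives two dose levels for a first afebrile grade 3 neutropenia that costs 5 or more of 21 doses or comes with a documented infection

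*Combined protocol and SAP*

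**What the plan says.** Table 4 in Section 6.2 sets the PD 0332991 dose from the worst treatment-related toxicity in the previous cycle. Three of its rows matter here.

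- **Afebrile grade 3 neutropenia.** The row "Grade 3 neutropenia without fever" holds the drug until the ANC is at least 1000/mm³. For the first occurrence the entry is "occurrence: resume at the same dose"; for the second and third it is a one-level reduction.
- **Complicated grade 3 neutropenia.** The row "Grade 3 neutropenia associated with a documented infection or fever" (38.5 °C or more) has the same hold, with recovery also from fever. The new dose level is "Decrease by one dose level", with no first-occurrence exception.
- **Delivery shortfall.** The row "Inability to deliver at least 80% of the planned dose of PD 0332991 or anastrozole due to adverse events possibly related to study treatment" also leads to "Decrease by one dose level", and it has no exception for neutropenia.

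The text above the table adds: "Doses omitted for toxicity are not replaced or restored within the same cycle". It also says that a patient who needs more than two reductions leaves the study. Neither Section 6.2 nor Section 6.3 says which row governs when two apply, and the period over which the planned dose is counted is not defined.

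**The concern.** A dose-modification table should send one event to one dose level. Here a neutropenia hold can itself create the delivery shortfall that another row penalises, so the same episode is told both to keep the dose and to lower it. The two grade 3 neutropenia rows also share a group of patients: those with a documented infection and no fever.

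The choice of row carries forward. A reduction taken at the first episode uses one of the two allowed before discontinuation. Sites that read the table differently could therefore give identical patients different doses and, after repeated episodes, different discontinuation decisions. The safety profiles during neoadjuvant and adjuvant therapy (secondary objectives 8 and 9) would then partly reflect which row a site applied. The question is still live: under Amendment 7 the endocrine resistant cohort remains open to enrolment, and eligible patients may receive up to 23 adjuvant cycles.

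**Working it through.** The plan states no figure of its own to reproduce, so this is a direct count of doses.

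**Inputs**
- Planned PD 0332991 doses in a full cycle: 21 (Days 1 to 21; Section 5.1 regimen table and Table 3).
- Threshold: at least 80% of the planned dose (Table 4).
- Held doses are lost (Sections 6.2 and 6.3).
- Unit of delay: one week (Section 6.3).

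**Situation 1: the hold causes the shortfall**

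Delivered share = (21 − missed doses) / 21. The delivery row is met when the share is below 0.80. Since 0.80 × 21 = 16.8, the row is met at 16 or fewer delivered doses.

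| Missed | Delivered | Share | Neutropenia row, first time | Delivery row |
|---|---|---|---|---|
| 4 | 17 | 81.0% | same dose | not met |
| 5 | 16 | 76.2% | same dose | one level down |
| 7 | 14 | 66.7% | same dose | one level down |

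Missed doses = the smaller of the hold length and (22 − start day).

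- A one-week hold starting by Day 15 costs 7 doses: 14/21 = 66.7%. Both rows are met.
- A hold starting on Day 17 can cost at most 22 − 17 = 5 doses: 16/21 = 76.2%. Both rows are met if all 5 are lost.
- A hold starting on Day 18 or later can cost at most 22 − 18 = 4 doses: 17/21 = 81.0%. No conflict.
- Neutropenia found on Day 1 of the next cycle, with a one-week delay, loses none of the 21 planned doses. Counted by calendar time instead, the cycle takes 35 days rather than 28, and 28/35 = 80.0%, which still satisfies the requirement. No conflict.

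**Situation 2: infection without fever**

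| First grade 3 neutropenia with | Infection-or-fever row | Without-fever row |
|---|---|---|
| fever | one level down | does not apply |
| no fever, no documented infection | does not apply | same dose |
| no fever, documented infection | one level down | same dose |

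Only the last line conflicts, and it does so at any hold length.

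**Where Situation 1 can arise.** As read from the extracted calendars, adjuvant Cycles 1 and 2 schedule a blood count on Day 14 (Section 10.3). If dosing is then held from Day 15 to Day 21, 14/21 = 66.7% is delivered. Neoadjuvant Cycles 1 to 4 show no mid-cycle count (Section 10.2), so a within-cycle hold for neutropenia there would need an unscheduled one.

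**The case against.** The best defence is that the rows are cumulative. The delivery row can be read as an extra criterion for prolonged holds, and the infection row as the specific case that takes its patients out of the without-fever row. Section 6.2 also describes its reductions as recommended. These readings are sensible, but the protocol states neither of them, and calling the table a recommendation does not tell a site which of two recommendations to follow.

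Much of the defence does limit the point. Four stronger readings are tempting, and the documents do not support them.

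- **That the delivery row cancels the same-dose step.** It does not in general. Short holds, late holds and neutropenia found on Day 1 of the next cycle leave that step intact.
- **That the conflict occurs almost every time.** The scheduled mid-cycle count exists only in adjuvant Cycles 1 and 2, and Section 6.3 allows restart within the cycle once counts recover, which implies a recheck. The 55% grade 3 neutropenia rate in Section 1.7 comes from a study with letrozole and is not split by fever or hold length, so it does not measure how often the rows collide.
- **That patients exit one episode earlier.** The rows differ only at the first occurrence. An earlier exit needs a first episode costing 5 or more doses and then repeated episodes, and Table 4 has no entry for a fourth. It is a worst case.
- **That the anastrozole trigger is a contradiction.** Section 6.1 says "No dose adjustment is permitted for anastrozole but interruptions are allowed per physician discretion", and Table 3 keeps anastrozole at 1 mg/day at every level. A shortfall in anastrozole therefore leads to a single stated action on PD 0332991, and no other passage gives a different one.

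**Conclusion.** The concern holds in two defined situations: a first afebrile grade 3 neutropenia that costs 5 or more of 21 doses (76.2% delivered or less), and a first grade 3 neutropenia with a documented infection but no fever. In each, two Table 4 rows give different dose levels and cannot both be followed. The first situation rests on counting the 80% against the 21 planned doses of one cycle, which the protocol does not state.

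The consequence is inconsistent dosing and discontinuation between sites, and hence safety summaries that are harder to interpret. The C1D15 reading for the primary endpoint falls within Cycle 1, before any reduction based on a previous cycle, so the sample size and error rates are unaffected. The documents give no distribution of hold lengths and no rate of infection without fever, so the frequency of either situation cannot be computed. No view is taken on which dose level is right.

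**What to change.** Reconcile these rows of Table 4 so that each event leads to one dose level:

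1. State which row governs when a neutropenia hold is itself the reason for delivering less than 80%.
2. Reword the two grade 3 neutropenia rows so that they are mutually exclusive, with infection without fever assigned to one of them.
3. State the period over which the 80% is counted.

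The investigators and the drug supplier decide which action applies in each case. The cost is a short protocol amendment to one table, with no added visits or tests.

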6.2.1 Dose Adjustments Due to QTc Prolongation

Any patients who develops new grade 2 or greater ECG QT corrected interval prolonged at any time during the study will need to have the ECG repeated immediately for confirmation.

Grade 2: no adjustments; continue at same dose level

Grade 3 (reversible cause identified and corrected): withhold treatment until QTc \leq 470 msec, then resume treatment at the same dose level

Grade 3 (no reversible cause identified): withhold treatment until QTc \leq 470 msec, then decrease PD 0332991 by one dose level

Grade 4: permanently discontinue PD 0332991

6.3 Re-Treatment Criteria for Neoadjuvant Cycles 1-4 and Adjuvant Therapy

A new cycle of treatment with PD 0332991 may begin only if:

- ANC \geq 1,000/mcL.
- Platelet count \geq 50,000/mcL.
- Non-hematologic toxicities have returned to baseline or Grade \leq 1 severity (or, at the Investigator's discretion, Grade \leq 2 if not considered a safety risk for the patient).

Criteria for dose interruption within cycle:

- ANC $<$ 1,000/mcL.
- Platelet count $<$ 50,000/mcL.

Re-treatment within the cycle may only be started when ANC \geq 1,000/mcL and platelet count \geq 50,000/mcL.

Doses omitted for toxicity within a cycle are not replaced or restored within the same cycle (meaning that the cycle remains 28 days regardless of the number of doses of taken).

If these conditions are not met, anastrozole treatment may be continued but treatment with PD 0332991 must be delayed by one week. If, after a one-week delay, all toxicities have recovered within the limits described above, treatment with PD 0332991 can be resumed.

If the patient has not recovered after 2 weeks (including the scheduled 1-week off treatment period within a cycle) despite dose reduction to the lowest dose level, treatment with PD 0332991 will be permanently discontinued.

Adjuvant PD 0332991 may be interrupted for a maximum of 4 weeks due to intercurrent illness or surgery (discuss with study chair).

Anastrozole is administered in a continuous regimen and therefore no re-treatment criteria apply.

6.4 Re-Treatment Criteria for Cycle 5

Cycle 5 Day 1 with PD 0332991 may begin only if:

- ANC \geq 1,500/mcL
- Platelet count \geq 100,000/mcL
- Non-hematologic toxicities have returned to baseline or Grade \leq 1 severity (or, at the Investigator's discretion, Grade \leq 2 if not considered a safety risk for the patient).

If these conditions are not met, anastrozole treatment will be continued but treatment with PD 0332991 will be delayed by one to three weeks. If all toxicities have recovered within the limits described above within 3 weeks, treatment with PD 0332991 for Cycle 5 will be initiated. If the patient has not recovered after a 3 week delay, treatment with PD 0332991 will be permanently discontinued and patients should proceed to surgery within 3 to 5 weeks after the last dose of PD0332991 (Cycle 4 Day 21) if possible.

Anastrozole is administered in a continuous regimen and therefore no re-treatment criteria apply.

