1.7 Rationale to Investigate PD 0332991 in Combination with Anastrozole

In preclinical studies, endocrine resistance was associated with persistent cyclin D expression and RB phosphorylation despite efficient blockade of ER and the poor prognosis luminal B breast cancers were associated with a gene expression signature of RB-dysfunction [20]. PD 0332991 was shown to have anti-tumor activity for multiple tumor types including breast cancer in both in vitro and in vivo studies [88, 89]. In preclinical studies, PD 0332991 was particularly effective in inhibiting cell growth of luminal breast cancer subtype [88]. A synergistic anti-tumor effect was also observed when combined with tamoxifen in tamoxifen-sensitive and resistant cell lines [88]. Importantly, treatment with PD 0332991 effectively suppressed proliferation of ER+ breast cancer cell lines resistant to anti-estrogen and led to irreversible cell cycle arrest and features of cellular senescence [20]. These studies provided a preclinical rationale to combine endocrine therapy and a Cdk4/6 inhibitor to improve tumor control for ER+ breast cancer.

[figure not shown]
The combination of PD 0332991 and endocrine therapy has shown highly promising results in patients with advanced ER+ HER2- breast cancer. In the randomized phase 2 study of letrozole with or without PD 0332991 as first line therapy for metastatic ER+, HER2- breast cancer, the PFS was significantly better in the combination arm (26.1 months vs 7.5

months (HR 0.37, 95% CI 0.21 – 0.63, $p<0.001$) [22]. The response rate for the combination arm ($n = 84$) was 31% vs. 26% for the letrozole arm ($n = 81$) and the clinical benefit rate was 68% vs. 44%, respectively. Toxicities were tolerable. The most commonly reported treatment-related AEs in the combination arm were neutropenia (grade 1/2: 23%; grade 3: 55%, grade 4: 6%), leukopenia (grade 1/2: 29%; grade 3: 17%, grade 4: 0%), anemia (grade 1/2: 24%; grade 3: 5%, grade 4: 1%), and fatigue (grade 1/2: 35%; grade 3: 2%, grade 4: 2%) and nausea (grade 1/2: 23%; grade 3: 2%, grade 4: 0%). The promising clinical data led to the FDA fast-track listing of PD 0332991.

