3.5 Eligibility Criteria for the Adjuvant Cohort

3.5.1 Inclusion Criteria

1. Derived benefit from PD 0332991 in the neoadjuvant setting in this trial. This includes the 26 patients who achieved complete cell cycle arrest only after the addition of PD 0332991 (C1D1 Ki67 >2.7% and C1D15 Ki67 \leq 2.7%) from the main study (PIK3CA WT, mutant, or unknown cohorts) as well as any patients who have a Ki67 \leq 10% on C1D15 biopsy in the endocrine resistant cohort.
2. ECOG performance status of 0, 1 or 2 (Appendix A).

3. If premenopausal, patient must be willing to comply with pregnancy requirements laid out in Section 5.5.
4. Adequate organ and marrow function as defined below:
 - a. leukocytes \geq 3,000/mcL
 - b. absolute neutrophil count \geq 1,500/mcL
 - c. platelets \geq 100,000/mcL
 - d. total bilirubin \leq upper normal institutional limits
 - e. AST(SGOT)/ and ALT(SGPT) \leq 2.5 X institutional upper limit normal
 - f. Creatinine \leq upper normal institutional limits
5. Underwent surgery of the breast and axilla for curative intent.
6. At least 4 weeks post completion of adjuvant chemotherapy and radiation therapy if indicated.
7. Patients who already started on adjuvant hormonal therapy are eligible under the following conditions:
 - a. For the 26 patients who enrolled in the initial cohorts and derived benefit from neoadjuvant PD 0332991 (C1D1 Ki67 $>2.7\%$ and C1D15 Ki67 $\leq 2.7\%$), adjuvant PD 0332991 should be initiated as soon as possible if adjuvant hormonal therapy has been initiated and the patient has completed radiation if indicated.
 - b. For patients who enrolled in the endocrine resistant cohort and derived benefit from neoadjuvant PD 0332991 (C1D15 Ki67 $\leq 10\%$), adjuvant PD 0332991 should be initiated within 6 months or sooner after initiation of adjuvant hormonal therapy.
8. Able to understand and willing to sign an IRB-approved written informed consent document.

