to recover to \leq grade 1 as well as to accommodate surgery scheduling. Anastrozole is continued in all patients during the neoadjuvant period. Patients who receive goserelin should also continue goserelin every 28 days during the neoadjuvant period.

CBC+D is to be performed 3 days (± 1 day) prior to surgery in patients who receive Cycle 5 therapy. Treatment with PD 0332991 should be interrupted if ANC $<$ 1,000/mcL, platelets $<$ 100,000/mcL, or patients present with any \geq grade 2 treatment-related toxicities. If a patient needs to stop treatment prematurely in Cycle 5, she will have surgery on the scheduled date unless contraindicated, as the recovery of neutropenia is usually prompt after stopping PD 0332991 due to its mechanisms of action (investigator brochure). However, surgery may be rescheduled at the discretion of the treating physician and the study chair. Patients should continue with anastrozole until the day before surgery regardless of whether they complete Cycle 5 of PD 0332991.

Patients whose ANC and/or platelets do not recover within 3 weeks following the completion of Cycle 4 will proceed to surgery as planned (3 to 5 weeks following the last dose of PD 0332991 (Cycle 4 Day 21)). For these patients, anastrozole is to be continued until the day of surgery, with the last dose of anastrozole given the day before surgery.

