10.2 Neoadjuvant Study Treatment Calendar (ALL Cohorts)

	≤ 14 days prior to registration	C1D1 ^A	C1D15 ±1 day	C2-5 D1±3 days	3 (+/-1) days prior to surgery	Off Study - Progression	Surgery ^B	Post-surgery ^C
TREATMENT								
Anastrozole ^E		Daily until the day of surgery (if no progression)						
Goserelin ^E		Every 28 days (if no progression)						
PD 0332991 ^F		3 weeks on and 1 week off ^{G,T}			D/C			
CLINICAL ASSESSMENT								
H&P, PS	X	X		X		X		X
Clinical meas. of breast lesions ^J	X	X		X		X		Exam
Adverse event assessment	X	X		X		X		X
CBC + differential	X			X	X ^Y			X
Serum chemistry ^K	X			X				X
Serum pregnancy test ^L		X			X	X		
Drug compliance assessment				X				
EKG (lead II) ^N	X						X	
RADIOLOGY								
Mammogram and US of breast and axillary masses ^O	X ^H			X ^H		X		
SAMPLE COLLECTION								
Tumor biopsies ^R		X ^W	X ^P	X ^Q		X ^S	X	
Research blood ^R		X ^U	X ^{P,V}			X ^S	X	

- A. C1D1 office visit, labs, EKG, as well as pre-PD 0332991 tumor biopsies may be done within 14 days prior to C1D1.
- B. Please refer to section 5.1. Surgery occurs between Cycle 5 day 11 and day 13 in patients who received Cycle 5 treatment. In patients who did not receive Cycle 5 treatment, surgery occurs 3 to 5 weeks following the last dose of PD 0332991.
- C. 30-60 days post-surgery, then yearly to document recurrence and survival for 5 years.
- E. Anastrozole (and goserelin if premenopausal) should have been started at least 28 days prior to C1D1 **(only applies to PIK3CA Mutant and Wild Type cohorts).
- F. Patients will keep a pill diary (Appendix D).
- G. If C1D15 Ki67 is > 10%, patient will discontinue PD 0332991 and be observed for AEs 30-60 days following the last dose, then followed per protocol. Further treatment is at the discretion of the treating physician.
- H. Prior to start of PD 0332991 (within 12 weeks prior to registration) and at the end of cycle 4 before surgery.
- J. 2D measurements of the breast lesion should be performed. Using a standard cm calibrated caliper, tape or ruler, the longest axis and the perpendicular axis of the tumor are to be measured and recorded in metric notation. In patients with synchronous lesions, it is recommended that both lesions be measured and biopsied the same if they are both >1cm with at least one dimension; otherwise, the dominant mass is followed clinically and by Ki67

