13.0 DATA AND SAFETY MONITORING

In compliance with the Washington University Institutional Data and Safety Monitoring Plan, the Data and Safety Monitoring Committee (DSMC) will meet to review toxicity data at least every 6 months following the activation of the first secondary site. The report will be prepared by the statistician with assistance from the study team and will be submitted to the Quality Assurance and Safety Monitoring Committee (QASMC). This report will include:

- HRPO protocol number, protocol title, Principal Investigator name, data coordinator name, regulatory coordinator name, and statistician
- Date of initial HRPO approval, date of most recent consent HRPO approval/revision, date of HRPO expiration, date of most recent QA audit, study status, and phase of study

- History of study including summary of substantive amendments; summary of accrual suspensions including start/stop dates and reason; and summary of protocol exceptions, error, or breach of confidentiality including start/stop dates and reason
- Study-wide target accrual and study-wide actual accrual including numbers from participating sites
- Protocol activation date at each participating site
- Average rate of accrual observed in year 1, year 2, and subsequent years at each participating site
- Expected accrual end date and accrual by site.
- Objectives of protocol with supporting data and list the number of participants who have met each objective
- Measures of efficacy
- Early stopping rules with supporting data and list the number of participants who have met the early stopping rules
- Summary of toxicities at all participating sites
- Abstract submissions/publications
- Summary of any recent literature that may affect the safety or ethics of the study

Until such a time as the first secondary site activates this protocol, a semi-annual DSM report to be prepared by the study team will be submitted to the QASM Committee beginning 6 months after study activation at Washington University.

The study principal investigator and Research Patient Coordinator will monitor for serious toxicities on an ongoing basis. Once the principal investigator or Research Patient Coordinator becomes aware of an adverse event, the AE will be reported to the HRPO and QASMC according to institutional guidelines.

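### Neoadjuvant Cycles 1-4 have a mandatory within-cycle hold for low counts but no scheduled on-drug blood count, so cytopenia that recovers in the off week can be missed

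*Combined protocol and SAP*

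**What the plan says.** Section 6.3 governs neoadjuvant Cycles 1-4 and adjuvant therapy. Under "Criteria for dose interruption within cycle" it lists ANC below 1,000/mcL and platelets below 50,000/mcL, and it allows restart in that cycle only once both have recovered to those limits. The same limits must be met before a new cycle begins.

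Table 4 in Section 6.2 is titled as giving "Dose Modifications Based on Worst Treatment-Related Toxicity in the Previous Cycle". Grade 4 neutropenia and grade 4 thrombocytopenia each lower the dose by one level. For afebrile grade 3 neutropenia the first entry is "occurrence: resume at the same dose"; the second and third occurrences each lower the dose.

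The Section 10.2 calendar marks a CBC at screening, at Day 1 (±3 days) of Cycles 2-5, about 3 days before surgery, and after surgery. Footnote Y limits the pre-surgery count to patients in Cycle 5. At C1D15 there is a tumor biopsy and research blood, but the CBC and adverse event rows are blank. Cycles 2-4 have no mid-cycle visit apart from an optional biopsy.

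The Section 10.3 calendar, under the same Section 6.3 rule, marks a CBC at D14 (±3 days) of adjuvant Cycles 1-2.

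**The concern.** A hold that depends on a count during the cycle needs such a count to be taken. In Cycles 1-4 every scheduled count comes after the drug-free week, and Section 5.1 states that "the recovery of neutropenia is usually prompt after stopping PD 0332991". A low count on drug can therefore be back within limits by the time anyone is scheduled to look.

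Three things are at stake:

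- The hold would not be applied when the protocol says it must be.
- A reduction for grade 4 or repeat grade 3 neutropenia could be missed, so the patient starts the next cycle at a dose that Table 4 would have lowered.
- Safety during neoadjuvant therapy is a secondary objective, and Section 15.5 summarizes the maximum grade per patient. That table can understate hematologic toxicity if counts are routinely taken only after recovery.

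A missed first afebrile grade 3 episode costs less: the hold itself, and its being counted as the first occurrence.

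**Working it through.** The plan states no figure of its own on this point, so there is nothing to reproduce. The check is a comparison of schedules with some simple arithmetic.

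**Scheduled on-drug counts**

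| Period | Hold rule | Scheduled on-drug CBC |
|---|---|---|
| Neoadjuvant Cycles 1-4 | Section 6.3 | none (Section 10.2) |
| Cycle 5 (10-12 days) | Section 5.1 | one, 3 (±1) days before surgery |
| Adjuvant Cycles 1-2 | Section 6.3 | one per cycle, D14 ±3 |
| Adjuvant Cycles 3-23 | Section 6.3 | no mid-cycle count |

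The CBC row in Section 10.2 reads cleanly against its header: the biopsy marks in the same table fall under the columns that their footnotes describe. No other section adds a count. Section 6.2 says only that toxicity will be monitored, and the every-cycle Labs Form in Section 11.0 is a data submission schedule.

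**Exposure without a scheduled count.** Dosing is Days 1-21 of 28 (Section 5.1). Four cycles give 4 × 21 = 84 dosing days, with 0 scheduled on-drug counts.

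**Distance of the routine count from drug.** The next Day 1 is Day 29 and the last dose is Day 21, so 29 − 21 = 8 days. With ±3 days the range is 5 to 11, assuming no cycle delay.

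**What the Day 1 count can trigger.** A count that is still low at Day 1 (±3) blocks the new cycle under Section 6.3 and can set the Table 4 dose. An event that has fully recovered by then does neither.

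**How common the event might be.** Section 1.7 reports treatment-related neutropenia of grade 3 in 55% and grade 4 in 6% with PD 0332991 plus letrozole in metastatic disease, without cycle days. Applied to all 37 planned endocrine resistant patients:

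- grade 3: 0.55 × 37 = 20.4
- grade 4: 0.06 × 37 = 2.2

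These are upper-bound illustrations. Only patients still to be enrolled are affected, and planned neoadjuvant exposure here is four full cycles and a short fifth. The share that would occur on drug and recover by Day 1 could be anything from none to all.

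**On-drug data in the protocol.** Section 2.0 gives a mean ANC of 2.2 to 4.2 k/mcL within 10-12 days of treatment, and 0 of 9 patients below 1,000 on Day 10. The one-sided 95% upper limit for 0 of 9 is 1 − 0.05^(1/9) = 0.283, or 28%. Nothing covers Days 13-21.

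**Coverage after a fix.** A count at C1D15 is preceded by 15 dosing days, leaving 84 − 15 = 69 with no later on-drug count in the cycle. Adding one at Day 15 of Cycle 2 covers 2 × 15 = 30 and leaves 54: Days 16-21 of Cycles 1-2 (6 × 2 = 12) plus all of Cycles 3-4 (2 × 21 = 42).

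**The case against.** The strongest reply is that the plan already handles part of this. The Day 1 count is a real trigger for Table 4 whenever cytopenia persists, and at the early end of its window it falls on Days 26-28, still inside the previous cycle. A reader might infer that the hematologic rows of Table 4 have no scheduled trigger at all; the documents do not support that. What lacks one is the within-cycle hold, and Table 4 only for events that recover in the off week.

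The hold also applies to any count that exists, including one drawn at the investigator's discretion. Toxicity forms are continuous, and the DSMC "will meet to review toxicity data at least every 6 months". These are genuine safeguards, but none supplies an on-drug count.

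A reader might also infer that the protocol contradicts itself, because adjuvant Cycles 1-2 have a D14 count under the same rule. It does not. From adjuvant Cycle 3 the CBC is marked only at every third cycle, sparser than the neoadjuvant schedule. The comparison shows that a mid-cycle count was thought worthwhile for patients already exposed to the drug in this trial, while endocrine resistant patients, who may not have had a Cdk4 inhibitor before, get none. That is a monitoring gap.

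Finally, no harm is demonstrated, and the available on-drug counts are reassuring as far as they go. That stands, and it limits the weight of the point. It does not remove the gap, since those data stop at Days 10-12 of a 21-day course.

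**Conclusion.** The concern holds as a gap in scheduled safety monitoring. In neoadjuvant Cycles 1-4 the Section 6.3 hold has 0 scheduled on-drug counts over 84 dosing days, and grade 3 or 4 cytopenia that is asymptomatic and recovers before Day 1 can escape both dose reduction and the Section 15.5 table.

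The conclusion rests on the calendar as printed and on cycles running without delay. The number of events missed cannot be derived, and the figures of about 20 and about 2 patients should not be read as an estimate of it. Nor do the documents support an inference that the primary result is compromised: Ki67 on C1D15 is measured whatever the CBC schedule. The point is a worthwhile, inexpensive improvement, relevant only to remaining endocrine resistant enrolment because the PIK3CA cohorts are closed.

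**What to change.** In Section 10.2, add a CBC with differential and an adverse event assessment at the C1D15 visit. Draw the count at the same visit as the biopsy and research blood, including when footnote P lets that visit move as late as C1D20. State that any hold is acted on as soon as the result is known and is not delayed for the biopsy.

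A Day 14-15 CBC in Cycle 2, matching adjuvant Cycles 1-2, is optional because that cycle has no scheduled mid-cycle visit and would need an extra draw. The safety report should also state on which cycle days counts were taken, so that readers can judge the maximum-grade table.

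The cost of the core change is calendar wording and one routine tube, with a small chance of a hold close to the biopsy. It does not cover Days 16-21 of Cycle 1 (when the visit is on time) or later cycles, and the documents do not show that Day 14-15 is the nadir.
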